## **STATISTICAL ANALYSIS PLAN**

Statistical analysis of the data will be limited given the small sample size. Given the scales used for evaluation, data will be recorded as continuous scores. Statistical analysis will be completed using non-parametric methods (with significant defined as  $p < 0.05$ ) due to the subjective nature of the quantitative scales of improvement used and possible skew of results. Given that multiple areas will be treated and monitored for improvement over time, we may need to apply the Bonferroni Correction. If and when dependent samples are reported (i.e. longitudinal measures on individual patients), analysis will be completed with either the Mann-Whitney-Wilcoxon Test (two observations) or Friedman's test (more than two observations). When possible, trend evaluated over time will be assessed using a non-parametric test for trends over ordered groups. Bonferroni correction will be used to account for multiple comparisons. Analysis will be completed using STATA, version 13.

Power and sample size will be determined based on primary outcome- to compare the improvement between ablative and non-ablative therapy in face, décolletage, hands, trunk, upper and lower extremities, and vagina. Given the 7 regions to compare, Bonferroni correction was used to define the new significance level as  $0.05/7=0.007$ . Sample sizes of 10 in ablative and 10 in non-ablative group in each body region achieve 81% power to show a difference in means when there is a difference of 2.0 between the null hypothesis mean difference and the actual mean at the 0.007 significance level (alpha) using a two-sided Mann-Whitney-Wilcoxon Test.

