The study endpoint will be 3 months. Number of laser treatments needed during this time period will be based on the patient's clinical response to each treatment (as assessed by the physician). Evaluation will occur using various validated methods including photographs, MPM imaging, the Global Aesthetic Improvement Scale, the Visual Analogue Scale, the Modified Fitzpatrick Wrinkle Scale, the Wrinkle Severity Rating Scale, the Facial Laxity Improvement Scale, the Dyspigmentation Scale, the Mid-Clavicular Nipple Distance, the Fabi Bolton Chest Wrinkle Scale, the Merz Hand Grading Scale, the Vulvo-vaginal Laxity Questionnaire, Female Sexual Function Index, International Consultation on Incontinence Questionnaire – Short Form, Severity of Alopecia Tool, Psoriasis Scalp Severity Index, Patient Global Impression of Change, and Clinician Global Impression (based on which body site and laser are used).

There are no composite variables as the primary outcomes will only be determined by the physician and subject GAISSs. Other criteria for evaluation (secondary and exploratory outcomes) include photographs, the Modified Fitzpatrick Wrinkle Scale, the Wrinkle Severity Rating Scale, the Facial Laxity Improvement Scale, the dyspigmentation scale, the mid-clavicular nipple distance, the Fabi Bolton Chest Wrinkle Scale, the Merz Hand

Grading Scale, the Visual Analogue Scale for pain, the patient diary, and the investigator-authored patient satisfaction survey.

At each study visit, the investigator/physician will collect physician and subject-reported data regarding the efficacy and adverse events associated with the procedure (Visits 2-5, Days 14-90). To define patient satisfaction, an investigator-authored survey will be completed at the last visit (Visit 5, Day 90). Photographs will be collected at all visits (Visits 1-5, Days 1-90).

Since use of the PALLAS laser is typically required twice weekly, treatment of scalp and hypopigmentation disorders will follow a separate schedule of events from the other energy-based devices. Subject will receive 24 treatments over 12 weeks (Visits 1-24), with patient and clinician assessments and clinical photos taken at every other visit (Visit 2, 4, 6, 8, 10, 12, 14, 16, 18, 20, 22, 24). A blinded clinician will also assess change in skin or hair at Visit 12 and 24. Visit 25 will consist of a one-month follow up after the three-month treatment period.

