Micro-coring (Ellacor) treatments are typically recommended in one month intervals so it will follow a separate schedule. Subjects will receive three treatments over two months (day 0, 30 and 60). Followup visits will be conducted at 1 month and 3 month post-last treatment (day 90 and day 150, respectively.) Patient and clinician assessments and clinical photos will be taken at every other visit.

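### For two observations on the same patient the SAP names the Mann-Whitney-Wilcoxon test, which is for independent samples and ignores the pairing

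*Combined protocol and SAP*

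**What the plan says.** The first paragraph of the Statistical Analysis Plan sets a rule for repeated measures. For dependent samples it reads "longitudinal measures on individual patients), analysis will be completed with either the Mann-Whitney-Wilcoxon Test (two observations"), and it assigns longer series to Friedman's test. A test for change over time is mentioned but not named: "trend evaluated over time will be assessed using a non-parametric test for trends over ordered groups".

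The second paragraph justifies 10 ablative and 10 non-ablative patients per body region, two different sets of patients, at a "significance level (alpha) using a two-sided Mann-Whitney-Wilcoxon Test".

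Two passages under Study Design bear on whether two-observation data will arise. For the PALLAS laser: "A blinded clinician will also assess change in skin or hair at Visit 12 and 24". For the micro-coring (Ellacor) schedule of five visits (Days 0, 30, 60, 90 and 150): "Patient and clinician assessments and clinical photos will be taken at every other visit".

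**The concern.** The Mann-Whitney-Wilcoxon test compares two independent groups. Its null distribution assumes that the two sets of scores are unrelated. Two scores from one patient usually are related, and a paired analysis gains precision by removing the variation between patients. The rank-sum test leaves that variation in.

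The SAP gives one test name to two data structures, and the name fits only one of them. An analyst following the text would run the unpaired test on paired data. An analyst who assumed a slip would run the signed-rank test. The plan does not settle which, so the choice could be made after the data are seen.

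With positive correlation the error is conservative. It risks missing real within-patient improvement in small secondary and exploratory analyses; it does not create false claims of benefit.

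**Working it through.** **The plan's own figure.** The SAP states 81% power for 10 versus 10, a difference of 2.0 and alpha 0.05/7 = 0.00714 (given as 0.007). No SD is stated, so this can be neither confirmed nor refuted. An exact Mann-Whitney test reaches 80.3% in simulation if the SD is about 1.1. The figure concerns independent groups, and nothing below depends on it.

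**Where two-observation data arise.**
- PALLAS blinded ratings: Visits 12 and 24, so two observations.
- Ellacor: if alternate visits means the even ones, Days 30 and 90, so two observations. If the odd ones, Days 0, 60 and 150, so three and Friedman's test.
- Any baseline versus Day 90 contrast would have two, but none is pre-specified.
- The standard laser schedule (Visits 1 to 5) and the optional multi-photon imaging (baseline plus three visits) give more than two and go to Friedman's test, which is suitable.

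**Direction of the error.** Let each visit have SD σ, with correlation ρ between visits and n patients. The standard error of the mean change is σ√(2(1−ρ)/n). Treating the visits as independent groups gives σ√(2/n). The ratio is 1/√(1−ρ):
- ρ = 0.3: 1/√0.7 = 1.20
- ρ = 0.5: 1/√0.5 = 1.41
- ρ = 0.7: 1/√0.3 = 1.83

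The rank tests behave in the same way.

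**Size.** The documents give no correlation, SD or within-patient effect. The simulations therefore assume normal scores with a shared patient effect and a 1-SD shift.

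Untied scores, n = 10 pairs, exact two-sided tests (power is rank-sum vs signed-rank):

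| ρ | Rank-sum type I error at 0.05 | Power at 0.05 | Power at 0.05/7 |
|---|---|---|---|
| 0 | 4.4% | 51% vs 50% | 23% vs 16% |
| 0.3 | 1.9% | 52% vs 64% | 21% vs 24% |
| 0.5 | 0.9% | 53% vs 78% | 19% vs 37% |
| 0.7 | 0.2% | 55% vs 94% | 17% vs 62% |

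The signed-rank type I error stays near 5% throughout. With n = 20 and ρ = 0.5, power is 92% vs 98% at 0.05 and 63% vs 89% at 0.05/7.

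Tied five-point scores (latent normal cut at −1, 0, 1 and 2), n = 10, power as rank-sum vs signed-rank. The rank-sum test uses the tie-corrected normal approximation throughout:

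| ρ | 0.05, zeros kept, normal approx. | 0.05, zeros dropped, exact | 0.05/7, zeros kept, normal approx. | 0.05/7, zeros dropped, exact |
|---|---|---|---|---|
| 0.3 | 52% vs 60% | 51% vs 48% | 16% vs 13% | 16% vs 7% |
| 0.5 | 52% vs 72% | 52% vs 58% | 14% vs 21% | 14% vs 10% |
| 0.7 | 53% vs 87% | 54% vs 74% | 13% vs 35% | 13% vs 16% |

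A smaller shift shows the same pattern. At 0.8 SD, n = 10, ρ = 0.5 and untied scores, power is 32% vs 60% and the median p-value 0.105 vs 0.037; the rank-sum p-value was the larger in 79% of simulated trials. With negative correlation the direction reverses: at ρ = −0.3 the rank-sum type I error is 7.4%.

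**The case against.** **It is probably a slip of naming.** The sentence identifies the data as dependent and sets the test beside Friedman's, and Wilcoxon's name belongs to both tests. This is plausible. But the text does not say signed-rank, and the next paragraph uses the same name for independent groups. A likely slip is a reason to correct the wording.

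**The rule has little documented use.** Most schedules give more than two assessments. No baseline versus Day 90 contrast is specified, and the primary measure is an improvement scale. Ellacor depends on how alternate visits are read. That leaves the PALLAS blinded ratings, for which no Visit 12 versus Visit 24 test is specified. The scalp is not among the regions in the sample-size paragraph, so 10 or 20 pairs is not a documented PALLAS sample size. All of this stands and limits the scope. The SAP's rule would still govern any such test.

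**The power gain can vanish.** With tied five-point scores at 0.05/7 and correlation 0.3, the signed-rank test has less power under either way of handling zeros; with zeros dropped and an exact test it also has less at 0.5. This is correct: the large gaps belong to untied scores, the 0.05 level and moderate to high correlation. It qualifies the size of the benefit but does not make an unpaired test valid for paired data.

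**Conclusion.** The concern holds: the rule for two dependent observations is wrong as written. It affects within-patient comparisons of exactly two observations. The primary ablative versus non-ablative comparison and the analyses assigned to Friedman's test are not affected.

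Under positive correlation, the expected case for repeated scores on one patient, the p-values are too large on average, though not in every data set. The loss ranges from none at zero correlation to a large one at 0.7 with untied scores, and the power ordering can reverse with heavy ties and a strict alpha. These sizes rest on assumed correlations, a 1-SD shift, underlying normal scores and 10 or 20 pairs. That the named test does not fit paired data rests on the SAP's text alone. The point should be fixed, chiefly because the correction costs so little.

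**What to change.** In the SAP's sentence on dependent samples, replace the Mann-Whitney-Wilcoxon test with the Wilcoxon signed-rank test for two observations. State how ties and zero differences are handled and whether p-values are exact, since the tied results show that this affects power. Keep Mann-Whitney for ablative versus non-ablative comparisons and Friedman's test for more than two observations.

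As a separate clarification that carries no weight in the conclusion, name the trend test. The present wording suggests, but does not settle, a test for independent groups. Because the same patients are seen at each visit, it should be a within-patient test, for example Page's test where visits are complete.

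The cost is one phrase, a sentence on ties and zeros, and the name of the trend test. No new data, patients or visits are needed.

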## Research Procedures

We expect that screening patients for inclusion in this study will take two to three months total. Subjects will be screened for participation from the patient population of the UC Irvine, Department of Dermatology. Once a subject is chosen as a possible candidate, the research study team will discuss with the patient whether they would like to participate in a research study comparing non-ablative and ablative energy devices for skin improvement. It will be made clear to patients that modalities such as Fraxel, Halo, Helios, Vbeam, and Pico have been found to be efficacious for improvement of the skin of the face or body while ThermiVa and DiVa have been found to be efficacious for rejuvenation of the vagina, and PALLAS for the scalp or hypopigmentation disorders. Patients will be told that photographs of their scalp, face, neck/décolletage, trunk, hands, upper and lower extremities, and /or vagina depending on the treatment site will be taken and will possibly be used for publications and presentations in the future; it will be made clear to patients that all efforts will be taken to de-identify the photographs. Risks will be explained thoroughly to patients. If patients decide that they would like to participate, they will be given a copy of the informed consent either to take home and read for up to 2 weeks, or if they feel comfortable reading in a private room to read for a maximum of 2 hours before obtaining a signature. Once patients consent to participation, they will be scheduled for their first visit, which may be as early as on the same day as their screening visit.

If eligible, patients may opt to have multiple sites treated during the study.

At their first visit (Visit 1, Day 1), patients' inclusion/exclusion criteria will be reviewed, demographic information will be obtained, physician-assessment performed, vitals assessed, and photographs (before and after treatment) will be taken. Patients will then receive the energy-based treatment in one or more areas. Information regarding the area treated, the device used and the machine settings will be recorded in detail. Patients will be given a diary to fill out to assess for side effects and the timeline of resolution.

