## **Study Design**

This study will be designed as a prospective clinical trial to compare various energy-based devices for the improvement of the scalp, face, neck/décolletage, trunk, hands, upper and lower extremities, and vagina. If patients meet the inclusion and exclusion criteria for multiple treatment areas, they will be allowed to receive treatment for multiple areas. The treating physician will decide which energy-based device is best-suited to address the patients' aging concerns; although patient preference will be taken into account, ultimately the treating physician is responsible for the correct assessment of the patients' needs, the use of the appropriate energy-based devices, and the final treatment. Although this may lead to some bias, patients will be treated in the most appropriate manner for their disease. Patients will be followed for 3 months post-treatment to determine if the procedure was efficacious for rejuvenation of the treatment anatomical area.

Per statistical considerations outlined below we will be comparing non-ablative and ablative devices. For each body area studied, 10 patients will be enrolled each into the non-ablative and the ablative device groups. The decision to treat and which device will be used will be made by the physician after careful consideration of a subject's rejuvenation concern(s). Multiple devices may be used due on one subject; for instance, a subject may require facial, body and/or vaginal rejuvenation, in which case one of the devices such as the Fraxel, Halo, Helios, Vbeam, or PicoWay would be used to address the face or body with the device picked based on the subject's needs or concerns, while either the ThermiVa or the DiVa would be used for vaginal rejuvenation, and PALLAS would be used for the scalp or hypopigmentation concerns.

A retrospective electronic medical record review will also be completed as part of this study to capture patients who were previously treated with any of the aforementioned modalities for rejuvenation of either the face, neck/décolletage, hands, trunk, upper and lower extremities and/or vagina.

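### The planned within-patient tests compare visits with each other; on the primary improvement score they do not test against 'no change', and no other planned test does, including for PALLAS on the scalp

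*Combined protocol and SAP*

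**What the plan says.** - **Primary outcome.** Under Study Design, "the primary outcomes will only be determined by the physician and subject GAISSs". The same section lists the scale as the Global Aesthetic Improvement Scale. The Statistical Analysis Plan justifies non-parametric methods by the "subjective nature of the quantitative scales of improvement used and possible skew of results".
- **Timing.** Study Design has the investigator collect "data regarding the efficacy and adverse events associated with the procedure (Visits 2-5, Days 14-90". For PALLAS, assessments fall at even visits from 2 to 24, with a follow-up Visit 25 and a blinded rating of change in skin or hair at Visits 12 and 24. Research Procedures does place an assessment at Visit 1: "demographic information will be obtained, physician-assessment performed, vitals assessed, and photographs (before and after treatment) will be taken".
- **Within-patient tests.** When dependent samples are reported, "analysis will be completed with either the Mann-Whitney-Wilcoxon Test (two observations) or Friedman's test (more than two observations". The plan then adds a third method, to be used where feasible: "trend evaluated over time will be assessed using a non-parametric test for trends over ordered groups".
- **Between-group test.** Power is given for ablative v non-ablative in seven regions (face, décolletage, hands, trunk, upper extremities, lower extremities, vagina) with a two-sided Mann-Whitney-Wilcoxon test at 0.007. The scalp is not listed.
- **Purpose of follow-up.** Study Design says patients are followed for three months "to determine if the procedure was efficacious for rejuvenation of the treatment anatomical area".

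**The concern.** An improvement score already expresses change from the pre-treatment state, so its natural null value is 'no change'. The plan's longitudinal tests ask something else: whether the score differs between visits. A device that works fully by Day 14 and holds its effect gives identical scores at each visit, which is exactly the null of Friedman's test and of the trend test. A device whose effect disappears by Day 90 gives scores that differ between visits, and both tests can be strongly significant.

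The between-group test does not fill the gap. Two equally effective classes and two equally ineffective classes both give a null result. For PALLAS on the scalp there is no ablative counterpart in the documents, so only the over-time tests are left. What is at stake is the stated purpose of follow-up: the plan specifies no test that asks directly whether the primary score shows improvement.

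**Working it through.** **1. The plan's own figures.** 0.05/7 = 0.00714, stated as 0.007: this agrees. The 81% power belongs to the between-group test, not to this point, and cannot be reproduced because no SD is given. It would need an SD of about 1.25 (normal approximation), 1.12 (t test) or 1.09 (t test with the 3/π efficiency factor for Mann-Whitney).

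**2. What each planned test takes as its null, on a score that is already a change.**
- Two observations: visit A = visit B.
- Friedman: all visits equal.
- Trend: no ordering over visits.
- Ablative v non-ablative: the two classes equal.

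None is 'score = no change'. If the mean is the same at every visit, the first three nulls are true whatever that mean is. This step needs no simulation.

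**3. Size.** Inputs from the documents: n = 10 per class and region; four follow-up visits (Visits 2-5) or 12 for PALLAS (even Visits 2-24); alpha 0.05 or 0.007. Assumptions: integer scores from -1 to 3 with 0 = no change, between-patient SD 0.5, within-patient SD 0.7, and n = 10 for PALLAS (no PALLAS sample size is stated). There were 1,500 simulated groups per row. The one-sample test is an exact Wilcoxon signed-rank test against 0 at the last visit; the trend test is of Page type. Entries are % significant at 0.05 (at 0.007).

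| Mean score over visits | Friedman | Trend | One-sample v no change |
|---|---|---|---|
| 4 visits, constant 0 | 4.5 (0.4) | 5.5 (0.5) | 1.3 (0.0) |
| 4 visits, constant +1.5 | 3.7 (0.5) | 5.6 (0.6) | 98.9 (63.1) |
| 4 visits, fading 2 to 0 | 99.8 (95.9) | 100 (99.7) | 1.6 (0.0) |
| 4 visits, rising 0.5 to 2 | 95.5 (74.5) | 99.1 (92.9) | 100 (93.9) |
| 12 visits, constant +1.5 | 4.3 (0.4) | 3.5 (0.5) | 99.2 (62.3) |
| 12 visits, rising 0 to 1.5 | 99.7 (97.0) | 100 (100) | 99.0 (62.5) |

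The constant +1.5 rows look like the constant 0 row for Friedman and trend. With other SD choices the pattern is the same: at constant +1.0 Friedman is about 4% and the one-sample test 66-75% at 0.05; for a fade from 1.5 to 0 Friedman is significant in 94-99.8%.

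**4. Blinded PALLAS rating.** It has two observations, Visits 12 and 24, so the two-observation rule compares them with each other. Taken as a paired signed-rank test, that comparison is significant at 0.05 in 1-2% of groups at constant +1.5, against 96-99% for the one-sample test.

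**5. Feasibility of the one-sample test.** With n = 10 and no zero scores, the smallest two-sided signed-rank p is 2/2^10 = 2/1024 = 0.00195, below 0.007. One test per class and region is 7 × 2 = 14 per rater, or 28 for the physician and subject ratings. 0.05/14 = 0.0036 can still be reached; 0.05/28 = 0.0018 cannot. The multiplicity rule therefore has to be settled with the test.

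**The case against.** **The primary aim is comparative.** The first stated outcome is to compare devices, the power statement is for ablative v non-ablative, and a between-group rank test suits a post-treatment change score. The sentence on dependent samples is conditional. This stands: nothing in the documents says that an efficacy conclusion will rest on Friedman's test. The gap is that no other planned test addresses whether the procedure worked.

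**A reader might infer that the planned tests cannot show benefit at all.** The documents do not support that. The first PALLAS assessment comes after at most two of 24 treatments, so it is close to a baseline. A score rising from there would be detected (last row of the table), as indirect, uncontrolled evidence.

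**A reader might infer that PALLAS has no efficacy test of any kind.** That is also too strong. The background counts UV lasers as non-ablative, PALLAS also treats hypopigmentation on the body, and Study Design enrols both classes for each body area studied. Body PALLAS patients are therefore not clearly excluded from the non-ablative group. Only the scalp is plainly outside the seven regions. Alopecia and scalp psoriasis severity scales could be compared with a Visit 1 value, if scored then.

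**That the GAIS has no baseline is an inference.** This stands. No anchors are given, and the schedule tables that Research Procedures refers to are not in the available text. The scale's name and the Visits 2-5 collection support the inference but do not prove it.

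**A fading score would be seen.** A trend test has a direction, and a decline would show in the data. The false-positive risk therefore arises only if a significant result over time is reported as efficacy without its direction.

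**The added test is uncontrolled.** This stands. Physician-selected patients rated by physician and self cannot separate device effect from expectation or regression to the mean.

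**Conclusion.** The point holds in a limited form. On the primary improvement score, every planned within-patient test compares visits, and none compares the score with 'no change'. A stable benefit leaves rejection near alpha (about 4% for Friedman at 0.05), while a fade to zero can be significant in 94-99.8% of groups. The class comparison answers its own question but does not show that either class improved. For PALLAS on the scalp, no test of the GAIS against 'no change' is specified, and the blinded Visit 12 and 24 rating has the same problem.

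The result for a stable benefit follows from the null hypotheses and needs no distributional assumption. The power figures rest on the assumed score range, SDs and n = 10. The 99% for the one-sample test applies at 0.05; at the plan's 0.007 it is about 62%. The whole point assumes that the GAIS is not scored before treatment. The sponsor should act on this, but it does not invalidate the main comparison.

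**What to change.** 1. For change scales (GAIS, Facial Laxity Improvement Scale, Patient Global Impression of Change, blinded change rating), name one endpoint visit for each schedule. Prespecify there a one-sample Wilcoxon signed-rank or sign test against 'no change', for each device class within region and for PALLAS.
2. Report the proportion improved with an exact confidence interval. At n = 10 this is informative but wide: 10 of 10 improved gives a 95% lower limit of 0.025^(1/10) = 69%.
3. State whether these tests fall under the Bonferroni correction or are supportive. With 28 tests in one family the signed-rank test could not reach significance at n = 10.
4. On change scales, use Friedman and trend tests only to describe time course, and report direction. Keep Friedman as an efficacy test for severity scales scored at Visit 1.
5. State the GAIS anchors and whether it is scored at Visit 1, the PALLAS sample size, and whether body PALLAS patients count in the non-ablative group.

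Cost: SAP wording and some further tests on data already planned, with no new visits. The one-sample result is uncontrolled and must be described as such.

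### Within-patient longitudinal analyses: Friedman's test drops any patient with one missed assessment, a modest loss over four follow-ups and a large one on the PALLAS schedule

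*Combined protocol and SAP*

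**What the plan says.** The Statistical Analysis Plan makes the repeated-measures analysis conditional: "If and when dependent samples are reported (i.e. longitudinal measures on individual patients"). Where it applies and there are more than two time points, the test is Friedman's "test (more than two observations"). The same paragraph adds, where feasible, a non-parametric trend test over ordered groups. It gives no imputation rule, no allowance for dropout and no method for incomplete visit records.

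Study Design gives the group size: "For each body area studied, 10 patients will be enrolled each into the non-ablative and the ablative device groups". For most lasers it places the physician- and subject-reported data at Visits 2-5. The PALLAS UV laser has its own schedule of 24 treatment visits, "with patient and clinician assessments and clinical photos taken at every other visit", followed by a one-month follow-up at Visit 25. Research Procedures confirms that clinician and patient assessments are made at that final visit.

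The power statement concerns a different analysis: "Sample sizes of 10 in ablative and 10 in non-ablative group in each body region achieve 81% power", "at the 0.007 significance level (alpha) using a two-sided Mann-Whitney-Wilcoxon Test".

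**The concern.** Friedman's test ranks each patient's scores across all time points, so a patient with a gap cannot be ranked on the same footing as the others. Unless another rule is written down, that patient is dropped and every score already collected from them is lost to the test. The more assessments a patient is scheduled for, the more likely at least one gap becomes. PALLAS patients attend twice weekly for 12 weeks and are scored 13 times, so this schedule is the most exposed.

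What is at stake is the within-patient account of change over time. With groups of about 10, discarding observed scores costs power in that analysis and restricts the Friedman result to patients who attended every assessment.

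**Working it through.** **No stated figure to reproduce.** The plan gives no number for Friedman's test. Its one power figure, 81%, belongs to the between-group comparison and cannot be checked because no standard deviation is stated. For a difference of 2.0, 10 per group and alpha 0.007, 81% needs an SD of about 1.25 (normal approximation) or 1.09 (t distribution with the rank-test efficiency factor 3/π). Nothing below depends on it.

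**Inputs from the documents**
- Patients per group per body area: 10 (Study Design).
- Assessments after treatment, most lasers: K = 4 (Visits 2-5, Study Design). K = 5 if the Visit 1 physician assessment is counted.
- PALLAS assessments: 12 even-numbered visits + Visit 25, so K = 13 (Study Design; Research Procedures).

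**Assumptions**
- Missed-assessment rate m of 2%, 5% or 10%. The documents give none.
- A PALLAS group of 10. The sample-size paragraph does not list the scalp among its regions, so this rests on the general statement in Study Design.
- All scheduled assessments enter one test.

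**Step 1. Independent misses.** Share of patients with complete data = (1 − m)^K.

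| K | m = 2% | m = 5% | m = 10% |
|---|---|---|---|
| 4 | 0.98^4 = 0.922 | 0.95^4 = 0.815 | 0.90^4 = 0.656 |
| 5 | 0.98^5 = 0.904 | 0.95^5 = 0.774 | 0.90^5 = 0.590 |
| 13 (PALLAS) | 0.98^13 = 0.769 | 0.95^13 = 0.513 | 0.90^13 = 0.254 |

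Out of 10 patients this leaves 9.2, 8.1 and 6.6 for K = 4; 9.0, 7.7 and 5.9 for K = 5; and 7.7, 5.1 and 2.5 for K = 13.

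The rate at which half the group is lost is m = 1 − 0.5^(1/K): 15.9% for K = 4 and 5.2% for K = 13.

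**Step 2. Misses clustered within patients.** With a beta-binomial model and intraclass correlation ρ, the share complete is B(a, b + K)/B(a, b), where B is the beta function, a = m(1 − ρ)/ρ and b = (1 − m)(1 − ρ)/ρ. For example, m = 5% and ρ = 0.1 give a = 0.45 and b = 8.55.

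| K | ρ | m = 5% | m = 10% |
|---|---|---|---|
| 4 | 0.1 | 0.838 | 0.696 |
| 4 | 0.3 | 0.873 | 0.757 |
| 13 | 0.1 | 0.654 | 0.421 |
| 13 | 0.3 | 0.782 | 0.607 |

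For PALLAS, clustering raises the complete share from 51% to 65-78% at m = 5%, and from 25% to 42-61% at m = 10%.

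**Step 3. What the loss does to the test.** This is a simulation with 10 patients, a linear rise over time, SD 1, independent misses and permutation p-values. The effect sizes are assumptions chosen for illustration.

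| Assessments, total rise | Full data | m = 5%: Friedman, complete patients | m = 5%: Skillings-Mack | m = 10%: Friedman, complete patients | m = 10%: Skillings-Mack |
|---|---|---|---|---|---|
| 13, 1.6 SD | 95% | 60% | 94% | 24% | 92% |
| 4, 1.5 SD | about 65% | 52% | 60% | 42% | 57% |

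With no true change, both tests rejected in about 4-6% of runs.

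**The case against.** **The powered comparison is untouched.** A reader might infer that missed visits would shrink the main ablative versus non-ablative comparison. The documents do not support that. It is a Mann-Whitney-Wilcoxon comparison between groups and does not need every visit. Friedman's test enters only if longitudinal measures are reported, and it carries no power claim. This stands and limits the point to the within-patient analyses.

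**Thirteen assessments and 10 per group are not linked in the plan.** The first belongs to PALLAS alone. The second belongs to a design comparing ablative with non-ablative devices, and the plan names no ablative comparator for PALLAS. Nor does it say whether Friedman's test would be run per group or pooled, or on all 13 assessments. The blinded PALLAS assessment has only two time points, so Friedman's test does not apply to it. This stands: the PALLAS counts are conditional. Pooling would change the counts but not the percentages.

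**Independent misses are close to the worst case.** Missed visits tend to cluster in the same patients, which reduces the loss. This stands, so the clustered range belongs beside the independent one. It still leaves roughly a fifth to a third of PALLAS patients out at 5% missed.

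**Friedman's test is not the only planned look at time.** The trend test need not require complete records, so it would be too strong to say that the whole time course would describe only full attenders. That is true of the Friedman result alone. The trend test is planned only where feasible and does not repair Friedman's test.

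**A missing-data rule could solve this without a new test.** Imputation or a shorter list of key visits would also keep patients. That is fair, but the plan contains neither, and naming a test that accepts gaps settles the matter directly.

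**Conclusion.** The point holds as a minor, cheaply corrected weakness in the conditional within-patient analyses. For most lasers the loss is modest: about 1 to 3 of 10 patients at assumed independent miss rates of 2% to 10%. It is substantial only on the PALLAS schedule, where about half of an assumed 10 would be lost at 5% and about three quarters at 10%. With clustered misses the PALLAS loss falls to 22-35% at 5% and 39-58% at 10%.

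These sizes rest on assumed miss rates, on an assumed PALLAS group of 10, and on every scheduled assessment entering one test. The documents do not support reading this as a threat to the stated 81% power, or as a loss of this size across all devices.

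**What to change.** In the Statistical Analysis Plan, replace Friedman's test with the Skillings-Mack test, using a simulated p-value, for more than two repeated observations. It uses every observed visit. On complete data without ties it equals Friedman's test. Ties are likely with rating scales, and the two may then differ slightly; the simulated p-value deals with ties and small groups.

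The cost is one line in the plan and a user-written Stata command. Whether that command runs in the planned version 13 cannot be checked from the documents and should be confirmed before the line is changed. No visit, procedure or sample size changes. Skillings-Mack still assumes that missed visits are unrelated to outcome, so it recovers precision but does not remove bias if patients who do poorly, or who do well, stop attending. Reporting the number of patients observed at each assessment would let readers judge that.
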